1. Calculate the 10 years incidence of total CVD, all-cause mortality and each major DM complication in Chinese DM patients in primary care.
2. Determine the risk factors that significantly predict total CVD, all-cause mortality and each major DM complication for Chinese DM patients in primary care.
3. Develop and validate risk prediction models for total CVD, all-cause mortality and each major DM complication for Chinese DM patients in primary care.
4. Develop a risk prediction nomogram and chart for the risk of total CVD, all-cause mortality for Chinese DM patients in primary care

Hypotheses

The following hypotheses will be tested:

1. Patient socio-demographic, clinical parameters, disease characteristics, and treatment modalities (these independent variables are described in the Methods section) are predictive of 10-year risk of total CVD, all-cause mortality and individual DM complication as a dependent variable.
2. The risk prediction models for total CVD, all-cause mortality and individual DM complication developed in this study can have over 70% of discriminating power.

d) **Plan of Investigation:**

(i) **Study design**

A 10-year retrospective study on a population-based cohort of Chinese DM patients in primary care.

(ii) **Subjects**

The cohort will include all patients with a documented clinical diagnosis of DM and were receiving care in the Hospital Authority (HA) primary care General Out-Patient Clinics (GOPC) and Family Medicine Clinics (FMC) on or before 1 July 2006 identified from the HA clinical management system (CMS) database.

Inclusion criteria

1. Age \geq 18 years old
2. At least 1 GOPC/FMC attendance on or within 1 year before 1 July 2006
3. Had a CMS record of the coding of ICPC-2 of T89 (Diabetes insulin dependent) or T90 (Diabetes non-insulin dependent) on or before 1 July 2006

Exclusion criteria

1. Patients who had a diagnosis of any DM complications defined by the relevant ICPC-2 or ICD-9-CM (shown in the Method section) on or before 1 July 2006.
2. Patients exclusively managed by Specialist Out-Patient Clinic (SOPC) on or before 1 July 2006.

Sample size calculation

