The detailed sample size calculation for each study outcome is attached in Appendix B. The required sample size is based on the requirements for the development and validation of the least common DM complication of ESRD. Specifically, based on our previous study, the 5-year incidence of ESRD was 1.9%(8), which can be extrapolated to a 10-year incidence of ESRD was 3.8% by assuming a constant incidence rate over time. To develop the risk prediction model for ESRD by multivariable Cox proportional hazard regressions with forward stepwise variables selection on 16 potential risks factors, we need 21,053 subjects using the 1 in 50 rule that 1 candidate predictor can be studied for every 50 events (23). To validate the risk prediction models, the area under the receiver operating characteristic curve (AUC) will be used to assess the discriminatory power of the predictive model on a separate sample of subjects. With 10 years incidence rate of ESRD was 3.8%(8), a total 14,307 subjects (544 subjects with ESRD and 13,763 subjects without ESRD) is needed to

ensure a precision of 0.05 for AUC of 0.7 by a 95% confidence interval.

Hence, a total 35,360 male and 35,360 female are needed for the development (training dataset) and validation of risk prediction models stratified by gender. The HA data set that we have obtained for our 5-year evaluation of quality of care and effectiveness of RAMP-DM study(8) has identified 120,857 DM patients under the care of public primary care on or before 1 Jan 2009, so we should be able to obtain sufficient number of subjects.

(iii) **Methods**

Each patient will be followed from 1 July 2006 to 31 December 2016 for the development of the indicator DM complications and mortality.

Definition of indicator DM complications

The incidence of four major DM complications (CHD, stroke, heart failure and ESRD), total CVD and all-cause mortality will be calculated. The incidence is counted from the earliest date of documented diagnosis defined by the relevant ICPC-2 and/ or ICD-9-CM coding recorded in the HA CMS database from 1 July 2006 to 31 December 2016. The relevant ICPC-2 and ICD-9-CM codes of each DM complication and mortality are determined by the academic and HA clinician co-investigators as listed below:-

1. CHD (ischaemic heart disease, myocardial infarction (MI), coronary death or sudden death) is defined by any of ICPC-2 K74 to K76 and ICD-9-CM 410.x, 411.x to 414.x, 798.x

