2. Stoke (fatal and non-fatal stroke) is defined by any of ICPC-2 K89 to K91 or ICD-9-CM 430.x to 438.x.
3. Heart failure is defined by any of ICPC-2 K77 or ICD-9-CM 428.x
4. CVD is defined as the presence of any of CHD, heart failure and stroke ICPC-2 or ICD-9-CM codes listed in 1, 2 and 3 above.
5. ESRD is defined by any of ICD-9-CM 250.3x, 585.x, 586.x, or an eGFR<15mL/min/1.73m².
6. Mortality is identified from the Hong Kong Death Registry.

Risk factors to be Included in the Risk Prediction Models

Risk factors (independent variables) previously found to be associated with DM

complications from the literature (4) and those that are routinely available in primary care are selected to strike a balance between comprehensiveness and feasibility. The potential risk factors that will be explored include those related to patient's socio-demographics, clinical parameters, disease characteristics and treatment modalities. Patient socio-demographics include sex, age and smoking status. Clinical parameters include body mass index (BMI), haemoglobin A1c (HbA1c), systolic and diastolic blood pressure, lipid profile (total cholesterol, HDL-C, LDL-C, triglyceride), estimated glomerular filtration rate (eGFR) and albuminuria. Disease characteristics include the duration of DM and co-morbidity. Treatment modalities include the use of specific anti-hypertensive drugs, insulin, specific oral anti-diabetic drugs and lipid-lowering agents. The operational definitions of the risk factors are shown in appendix A. These factors, except sex, age, duration of DM and co-morbidity, are modifiable, which have implications for practice.

Data collection

In the middle of 2017, anonymous data from 1 January 2006 to 31 December 2016 of all DM patients who satisfy the inclusion criteria and without any exclusion criteria will be extracted by the HA statistics team from the HA clinical management system (CMS) database. We have successful experience in working with the HA in the extraction of similar data from 2009 to 2013 for our extended evaluation on quality of care and effectiveness of RAMP-DM study (7), and we have obtained preliminary agreement from the HA for the data extraction in the present study.

Outcome Measures

1. The incidence of total CVD, all-cause mortality and each of 4 major DM complications over 10 years
2. Factors predictive of total CVD, all-cause mortality and each of 4 major DM complications over 10 years

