Multiple imputation will be used to handle missing data. Multiple imputation aims at increasing the power of the analysis and producing more reliable and applicable models within clinical practice. It also takes subjects with incomplete data into account to avoid unnecessary biases. Each missing value will be imputed five times by the chained equation method, which was equivalent to attain a relative efficiency of 95%. For each of the five imputed datasets, the same analysis will be performed with the five sets of results combined based on Rubin's rules.

2. Misclassification bias from the use of administrative database

This study relies on doctor entries of clinical diagnosis on DM complications and co-morbidity indicated by pre-defined by ICPC-2 and ICD-9-CM codes, which may be subject to misclassification bias. We will cross-check the diagnosis and prescription relation, and compare diagnosis from hospital and primary care records for the same patient in order to assess the data quality.

[Word Count: 3698]

e) Timetable of Work

June – August, 2017:

- i. Recruitment, training of RA
- ii. Meeting and discussion with HA co-investigators and Statistics team to confirm the data extraction schema and operation definitions

September – December, 2017

- i. Extraction of data from HA CMS
- ii. Update literature review

January – March, 2018:

- i. Data cleaning
- ii. Data analysis on the incidence & risk factors of DM complications and mortality

April – December, 2018:

- i. Data analysis to develop 6 prediction models
- ii. Validation of the prediction models

January -May 2019:

- i. Development of 10-year CVD risk prediction nomograms
- ii. Development of 10-year CVD risk prediction charts
- iii. Preparation of manuscripts for publications
- iv. Preparation of final report.

f) Existing Facilities:

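### The 95% relative efficiency claimed for five imputations depends on a fraction of missing information that the plan does not state

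*Combined protocol and SAP*

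**What the plan says.** Under Strategies against anticipated problems, item 1 (Missing data of risk factors), the plan adopts multiple imputation: "Each missing value will be imputed five times by the chained equation method, which was equivalent to attain a relative efficiency of 95" per cent. For each completed dataset "the same analysis will be performed with the five sets of results combined based on Rubin's rules". Neither this item nor any other section states a fraction of missing information, an expected percentage missing for any risk factor, or the share of patients with complete records.

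Three statements elsewhere in section d) bear on how much may be missing:

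- Subjects, inclusion criterion 2: "At least 1 GOPC/FMC attendance on or within 1 year before 1 July 2006".
- Methods, opening sentence: "Each patient will be followed from 1 July 2006 to 31 December 2016".
- Methods, Data collection: the extract will hold "anonymous data from 1 January 2006 to 31 December 2016 of all DM patients" who meet the criteria.

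The measurement definition of each predictor is deferred: "The operational definitions of the risk factors are shown in appendix A". That appendix is not in the text available for review.

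**The concern.** The sentence reads as if five imputations deliver 95% whatever the data look like. They do not, because the same five give more or less than 95% depending on how much information about a coefficient is missing. A reader cannot tell whether five was chosen for an expected level of missingness or simply taken as a default.

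The number of imputations matters more here than in an analysis with one pre-set model. The models are built by forward stepwise Cox regression, tests are at the 5% level, and there are six outcomes with men and women analysed separately. The risk charts then keep at most five of the most significant predictors. With few imputations, pooled coefficients and their p-values carry simulation noise from the random seed, and a borderline predictor may enter or drop out because of it.

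The dates raise a linked question. The extract covers less time before baseline than the eligibility look-back does, which may add to missing baseline values that could have been obtained.

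**Working it through.** **Inputs.** m = 5 and a stated relative efficiency of 95% (Missing data of risk factors); baseline 1 July 2006 (Methods); extraction start 1 January 2006 (Data collection); one-year attendance look-back (Inclusion criteria). Gamma is not in the documents, so it is varied as an assumption.

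**1. Can the 95% be reproduced?** Not from the plan's own inputs. It can only be inverted. On the variance scale RE = 1/(1 + gamma/m), so gamma = m × (1/RE − 1):

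- RE = 0.95, m = 5: gamma = 5 × (1/0.95 − 1) = 0.263.
- If 95% is rounded from 94.5%: gamma = 5 × (1/0.945 − 1) = 0.291.
- On the standard-error scale, RE = (1 + gamma/m)^(−1/2), so gamma = 5 × (1/0.95² − 1) = 0.540.

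The plan does not name its scale. On either scale the figure is conditional on a gamma that is not given.

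**2. Efficiency over an assumed range (variance scale).**

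| Assumed gamma | RE, m = 5 | RE, m = 20 | Smallest m for 95% |
|---|---|---|---|
| 0.3 | 94.3% | 98.5% | 6 |
| 0.5 | 90.9% | 97.6% | 10 |
| 0.7 | 87.7% | 96.6% | 14 |

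The last column is gamma/(1/0.95 − 1) = 19 × gamma, rounded up. Since gamma cannot exceed 1, 20 imputations give at least 1/(1 + 1/20) = 95.2%. At that number the plan's statement would hold without a condition.

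**3. Simulation noise in a pooled coefficient.** With between-imputation variance B and total variance T under Rubin's rules, the part of T due to using finitely many imputations is B/m. Its share of T is 1 − RE, so the Monte Carlo SD in units of the pooled standard error is about √(1 − RE):

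- gamma 0.3: √(1 − 0.943) = 0.24 with m = 5; √(1 − 0.985) = 0.12 with m = 20.
- gamma 0.5: √(1 − 0.909) = 0.30 with m = 5; √(1 − 0.976) = 0.16 with m = 20.

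So at gamma 0.5 a z statistic can move by about 0.3 from the seed alone. That can change the selection of a predictor close to the 5% boundary, but not of one far from it. This assumes that selection tests are made on pooled coefficients.

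**4. Dates.** From 1 January to 1 July 2006 is 181 days. The look-back from 1 July 2005 is 365 days, so 365 − 181 = 184 days of it (1 July to 31 December 2005) lie outside the extract. A patient whose last GOPC/FMC visit before baseline fell in those days meets criterion 2 and has no pre-baseline clinic reading in the extract. The documents do not say how many such patients there are.

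**The case against.** The best defence is that 95% with m = 5 is consistent with gamma of about 0.26, so what is missing is a stated assumption and the formula has not been misapplied. That stands. On the standard-error scale the bound is 54%, and even gamma = 0.5 gives 95.3%. That also stands, although the variance scale is the usual one.

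A reader might infer that missing information is likely to exceed 26%, or that about half of patients lack a baseline laboratory value because the extract covers only six months before baseline. The documents do not support either. They give no missingness rate and no testing frequency. The six-month window is inferred from dates, while the predictor definitions sit in Appendix A. The Introduction also raises averages of all readings, or the last reading before the event, as possible predictors, and the analysis section does not settle the matter. Nor is the percentage missing the same as gamma. The candidate list includes several related measurements (four lipid values, two blood pressures, eGFR and albuminuria), so gamma is usually below the missing share, and it differs by coefficient.

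The loss is also modest. At gamma = 0.5 the standard error is √1.1 = 1.05 times its value with unlimited imputations, and at 0.3 it is √1.06 = 1.03 times. The plan requires 35,360 patients of each sex, so strong predictors will hardly be affected. It would be wrong to read this as a source of bias.

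What survives is that the figure is stated without its condition, that substantial missingness is plausible (the plan itself lists it as an anticipated problem), and that borderline selections are exposed to seed noise at little saving.

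**Conclusion.** The point holds as a minor one. The unconditional 95% is unsupported: on the variance scale it needs gamma of about 26% or less, on the standard-error scale 54% or less, and the plan gives no gamma. Under assumed gammas of 0.3 to 0.7, five imputations give 94% to 88% efficiency on the variance scale. Whether the cohort falls in that range cannot be determined from the documents. The consequence is some loss of precision and less reproducible stepwise selection for borderline predictors.

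The mismatch between the one-year look-back and the extraction start follows directly from the stated dates. Its effect on missingness cannot be sized without Appendix A and the attendance data.

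**What to change.** 1. Use more imputations. Twenty is a convenient choice, because it secures at least 95% on the variance scale for any gamma. Alternatively, estimate gamma for each candidate predictor from a first imputation run and set m to at least 19 times the largest value.
2. Replace the unconditional 95% with the efficiency computed from the observed fraction of missing information, name the scale, and report the percentage missing for each predictor.
3. If the database holds the data, start the extraction on 1 July 2005 so that it matches the attendance look-back. The Timetable already has a meeting with the Hospital Authority to settle the extraction schema and definitions before extraction, and the change can be raised there.

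Items 1 and 2 cost computer time and a sentence or two of text. Item 3 changes the extraction request. The documents do not show that 2005 data are available, nor whether the budgeted HK$150,000 service charge would cover the extra months, so both need to be asked. Items 1 and 2 do not depend on item 3.

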3. 10-year risk prediction models for total CVD, all-cause mortality and each of 4 major DM complications
4. Factors that have sufficient power to classify Chinese DM patients in primary care into risk group in terms of total CVD and all-cause mortality.

(iv) **Data processing and analysis**

The cohort will be stratified by gender. Descriptive statistics will be used to calculate the incidence of total CVD, all-cause mortality and each of 4 major DM complications will be analysed annually and cumulatively over 10 years with a 95% confidence interval. The distribution of risk factors will be cross-tabulated by complication or mortality events. The 10 year cumulative incidence of various DM complications and mortalities will be further analysed by Kaplan-Meier method. The Kaplan-Meier survival curve will be used to describe the survivorship of total CVD, all-cause mortality and each of 4 major DM complications in the study cohort over 10 years. Unadjusted associations between the risk factors and odds of events will be assessed by independent t-test for continuous variables or Chi-square test for categorical variables.

The cohort will be randomly split on a 2:1 basis, with the two-third sample used for developing the risk prediction models, and the other one-third sample used for validation of the risk prediction models. The analyses will be carried out separately for men and women.

Development of risk prediction models

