Cox proportional hazard regressions with forward stepwise method will be used to develop the risk prediction models for total CVD, all-cause mortality and each of 4 major DM complications. If the main term of a clinical parameter is selected in the models, the quadratic term of such clinical parameter will be evaluated. Afterwards, the interaction terms between selected predictors and age will be also examined in the risk prediction models. Cox regressions is the most commonly used method in risk prediction models in the Framingham Heart Study (9, 10) and UKPDS (11, 12). It allows us to estimate the risk of disease or death for an individual, given their prognostic variables. A positive hazard ratio means a higher likelihood of event associated with that specific variable. Conversely, a negative hazard ratio means a lower likelihood of the event associated with that specific variable. The key proportional hazards assumption will be assessed by examining plots of the scaled Schoenfeld residuals against time for the covariates. Any non-random pattern indicates a violation of the proportional hazards assumptions in which case transformation of covariates may be considered. For example, all continuous variables were naturally logarithmically transformed to minimize the influence of extreme values and to

improve discrimination and calibration of the models. A parametric approach such as exponential or Weibull distribution for the hazard function can also be carried out. A total of 6 risk prediction models will be established for total CVD, all-cause mortality and each of 4 major DM complications. The log of the hazard ratio of each selected risk factor in the final model will be used as coefficient weights in the prediction model of each relevant outcome. The risk equations for 10 year's follow-up will be established by combining these weights with the survivor function(9). A receiver operating characteristic (ROC) curve of predicted risk against observed events will be used to determine the risk threshold for the predicted outcomes as the risk threshold with the highest sum of sensitivity and specificity of the actual observed events.

Validation of risk prediction models

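### Forward stepwise selection and Rubin's rules are combined without a rule for reaching one common set of predictors, so terms near the entry cut-off can leave no single final model to pool

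*Combined protocol and SAP*

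**What the plan says.** Under Strategies against anticipated problems, item 1 (missing data of risk factors), the plan states: "Each missing value will be imputed five times by the chained equation method, which was equivalent to attain a relative efficiency of 95"%. For each imputed data set, "the same analysis will be performed with the five sets of results combined based on" Rubin's rules.

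Under Development of risk prediction models in section d)(iv), the analysis has three data-driven stages:

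1. "Cox proportional hazard regressions with forward stepwise method will be used to develop the risk prediction models".
2. "If the main term of a clinical parameter is selected in the models, the quadratic term of such clinical parameter will be evaluated".
3. Then "the interaction terms between selected predictors and age will be also examined in the risk prediction models".

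The same section needs one end product for each outcome: "The log of the hazard ratio of each selected risk factor in the final model will be used as coefficient weights". It also says "A total of 6 risk prediction models will be established", and section d)(iv) adds "The analyses will be carried out separately for men and women". With six outcomes and two sexes, selection is carried out 6 × 2 = 12 times.

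The documents give no rule for reaching one predictor set across the imputed data sets: no pooled test at each step, no majority rule, no stacked data. They do not say whether selection comes before or after pooling.

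**The concern.** Rubin's rules combine estimates of one parameter from one model fitted in every imputed data set. If the analysis repeated in each set is itself a search, the sets can finish with different main effects. Because the quadratic and interaction stages depend on the main effects selected, they can then diverge further. A coefficient present in three sets and absent from two has no defined pooled value. Averaging it over the three sets tends to overstate it, and entering zero for the other two is not Rubin's rule.

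There is a second, smaller problem. A selection test inside one imputed set treats the imputed values as observed. Its standard error omits the between-imputation variance, so the test is too liberal for variables with many missing values.

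At stake is which terms enter the 12 risk equations, and hence the nomograms built on them. Without a stated rule, that choice would be made after the five sets of results have been seen.

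**Working it through.** **The plan's own figures.**
- Development size for end-stage renal disease (ESRD) per sex: 16 candidates × 50 events / 0.038 = 21,053, as stated under Sample size calculation. This corresponds to 21,053 × 0.038 = 800 events.
- Relative efficiency of m imputations is 1/(1 + λ/m), where λ is the fraction of missing information. With m = 5, 95% requires λ = 5 × (1/0.95 − 1) = 0.26. Efficiency is 0.980 at λ = 0.1 and 0.943 at λ = 0.3. The stated 95% is thus consistent with λ near 0.26, but the plan gives neither λ nor a missing-data rate.

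**Agreement of five sets on one term.** Scale the total pooled variance to 1. The within-imputation variance is then W = 1 − λ. The between-imputation variance is B = λ/(1 + 1/5) = λ/1.2. Centre the five estimates on the pooled z, with variance B. A term enters in one set if |estimate|/√W exceeds 1.96. The 5% entry level is an assumption: the plan sets 5% for all tests and no separate entry level. If p is the chance of entry in one set, all five sets agree with probability p⁵ + (1 − p)⁵.

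*λ = 0.3:* W = 0.70, B = 0.25, √B = 0.50. The cut-off on the estimate is 1.96 × √0.70 = 1.64.
- z = 1.5: p = P(N > (1.64 − 1.5)/0.5) = P(N > 0.28) = 0.39; agreement 0.39⁵ + 0.61⁵ ≈ 0.09.
- z = 1.96: p = 0.74; agreement ≈ 0.22.
- z = 3: p = 0.997; agreement ≈ 0.98.

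*λ = 0.1:* W = 0.90, B = 0.083, √B = 0.289, cut-off 1.86.
- z = 1.5: p = 0.107; agreement ≈ 0.57.
- z = 1.96: p = 0.64; agreement ≈ 0.11.
- z = 3: agreement above 0.99.

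At the other end, a term with z = 0 is left out of all five sets more than 99% of the time at either λ.

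**How liberal the within-set test is.** Under the same variance model, an estimate from one imputed set has variance W + 2B, but the test uses W. For a null term the true error of a nominal 5% test is 2 × P(N > 1.96 × √(W/(W + 2B))). This is about 7%, 10% and 13% at λ = 0.1, 0.2 and 0.3. It describes selection in a single set; a majority or all-sets rule would behave differently.

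**Whether the planned size removes the problem.** A simulation used 21,053 subjects, 800 events and 16 candidates (pairwise correlation 0.2). Eight candidates had values missing completely at random. There were five chained-equation imputations, forward Cox selection at p < 0.05 in each, and 60 replicates per cell. Effect sizes and missingness are assumptions.

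| Missing per affected variable | 5% | 10% | 20% | 30% | 40% |
|---|---|---|---|---|---|
| Graded effects (log HR per SD 0 to 0.5): sets not all identical | 67% | 82% | 93% | 95% | 97% |
| Ten equal effects of 0.3, six nulls: sets not all identical | 30% | 35% | 55% | 67% | 82% |

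The mean number of predictors in dispute was 1.0 to 2.9 in the graded case and 0.3 to 1.4 in the other. The Monte Carlo standard error is at most about 6 points. Only main effects were simulated; the quadratic and interaction stages add chances to diverge.

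**The case against.** The strongest reply is that the plan does not literally say that the stepwise search is repeated separately in each imputed set. The missing-data text could mean that one agreed model is fitted in each set, which is what Rubin's rules require, and the development section does speak of one final model. That reading is possible. It does not repair the plan, because the text would then be silent on how the agreed model is chosen from incomplete data.

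The second reply concerns size, and most of it stands. Disagreement is concentrated near the entry cut-off and depends on λ; at z = 1.5 it is far less common with λ = 0.1 than with λ = 0.3. Strong predictors enter every set. Disputed terms are mostly weak and should carry little weight in the risk equation. The charts use at most five of the most significant predictors, where agreement is most likely. The simulation is set at the minimum event count for the rarest outcome, not at total CVD or mortality.

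A reader might infer that the procedure always fails, or that five complete models almost never agree. The documents do not support either. When the five runs select the same terms, the coefficients can be pooled. A near-zero chance of full agreement would need several independent borderline terms with substantial missing information, and the plan gives no basis for assuming either.

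**Conclusion.** The point holds as a defect in the stated procedure. On the plain reading of the two sections, the rule gives no single model whenever the imputed sets select different terms, and the within-set selection test leaves out imputation uncertainty. No other part of the document supplies the missing step.

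The size is limited to terms near the cut-off. There, agreement of all five sets ranges from about 9% to 57% over the λ and z values shown for z = 1.5 and 1.96; at z = 3 it is 98% or more. These figures rest on an assumed λ, a 5% entry level and a normal approximation. A reader might go further and conclude that the models would discriminate or calibrate poorly. Nothing in the documents or in this check shows a change in AUC, calibration or predicted risk. The change is worth making because it is cheap and fixes the choice of terms before the results are known.

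**What to change.** In the model-development text and the missing-data text, state that one common set of main, quadratic and age-interaction terms is chosen across all five imputed data sets. At each forward step, test each candidate with the Rubin-pooled Wald statistic, and state the entry level. Then refit that fixed model in all five sets and pool the coefficients and the baseline survival.

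A majority rule stated in advance, followed by the same fixed refit, would also give one model. It would not by itself bring imputation uncertainty into the selection test.

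The cost is revised wording and longer run time across the 12 outcome-by-sex models. No new data are needed.
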